	
 – The elimination half-life ($T_{1/2}$) – The total area under the Concentration vs. Time curve from 0 to infinity (AUC_{0-168}) – The time to maximum drug concentration in the serum (T_{max}) – The residual area – The elimination constant (k_{el}) – The total clearance (CL). 
Methods used for PK assessment: The PK analysis will include all subjects who have received all doses of the test/reference drug as per protocol. Not more than 2 PK blood collections after the first injection and not more than 2 PK blood collections after the fourth injection can be missed. Subjects who have two consecutive blood samples missed will be not included in the analysis. The PK parameters will be analyzed based on darbepoetin alfa concentrations in the subject’s serum.

PD Endpoints
	
Endpoints:
 
 • Primary endpoint: 
 — The area under the baseline-adjusted Effect vs. Time curve from injection to Day 29 after the repeated-dose IV administration of the test/reference drug ($AUEC_{(1-29)}$). • Secondary endpoints: 
 — The maximum increase in hemoglobin from baseline, estimated from injection to Day 29 after the repeated-dose IV administration of the test/reference drug ($AC-E_{max}$). 
Supplementary endpoints:
 
 — The time to the absolute maximum increase in hemoglobin from injection to Day 29 after the repeated-dose IV administration of the test/reference drug (T_{max}). 
In addition, PD parameters ($AUEC$, $AC-E_{max}$, and T_{max}) will be estimated based on the reticulocyte and RBC counts and on hematocrit values.
 
Methods used for pharmacodynamic assessment:

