### **3.2. Time Points for Blood Sampling to Evaluate PK and PD**

In this study, blood samples will be collected according to the schedule to measure the concentration of darbepoetin alfa, evaluate the hemoglobin-based PD parameters, and to evaluate additional characteristics of the red blood (reticulocytes, RBC, hematocrit). The study also involves procedures to monitor the safety.

Blood samples for darbepoetin alfa concentration will be collected before and after each IV injection of the test/reference drug.

Collections will be performed as follows:

- Visit 1 (Day 1 – Day 2): 30 min, 20 min, 10 min and immediately before the first injection of darbepoetin alfa and then 5 min, 10 min, 15 min, 20 min, 30 min, 45 min, 1 h, 2 h, 4 h, 8 h, 16 h, and 24 h after the first injection.
- Visit 2 (Day 3): 48 h after the first injection.
- Visit 3 (Day 4): 72 h after the first injection.
- Visit 5 (Day 8): immediately before the second injection.
- Visit 9 (Day 15): immediately before the third injection.
- Visit 13, (Day 22 – Day 23): 30 min, 20 min, 10 min and immediately before the fourth injection of darbepoetin alfa and then 5 min, 10 min, 15 min, 20 min, 30 min, 45 min, 1 h, 2 h, 4 h, 8 h, 16 h, and 24 h after the fourth injection.
- Visit 14 (Day 24): 48 h after the fourth injection.
- Visit 15 (Day 25): 72 h after the fourth injection.

Blood samples for PD study will be collected as follows:

- Visit 1 (Day 1 – Day 2): before the injection and 24 h (one day) after the first injection.
- Visit 3 (Day 4): 72 h (3 days) after the first injection.
- Visit 4 (Day 6): 120 h (5 days) after the first injection.
- Visit 5 (Day 8): 168 h after the first injection (immediately before the second injection).

- Visit 6 (Day 9): 192 h after the first injection (24 h after the second injection).
- Visit 7 (Day 11): 240 h after the first injection (3 days after the second injection).
- Visit 8 (Day 13): 288 h after the first injection (5 days after the second injection).
- Visit 9 (Day 15): 336 h after the first injection (immediately before the third injection).
- Visit 10 (Day 16): 360 h after the first injection (one day after the third injection).
- Visit 11 (Day 18): 408 h after the first injection (3 days after the third injection).
- Visit 12 (Day 20): 432 h after the first injection (5 days after the third injection).

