#### **4. EVALUATION CRITERIA**

##### **4.1 Pharmacokinetics endpoints**

- $AUC_{(0-72)}$  (area under the plasma concentration curve from the moment of injection of darbepoetin alfa to 72 h after the first and the fourth IV injections of BCD-066 or Aranesp®)
- $C_{max}$  (the maximum concentration of darbepoetin alfa in the serum after the first and the fourth IV injection of BCD-066 or Aranesp®)
- The elimination half-life ( $T_{1/2}$ )
- $AUC_{0-\infty}$  (area under the plasma concentration curve from 0 to infinity)

- $T_{max}$  (the time to maximum drug concentration in the serum)
- The residual area
- $k_{el}$  (the elimination constant)
- CL (the total clearance)

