#### 8.4. Multivariate Comparison

Pharmacokinetic parameters

Based on determined concentrations in blood a number of the pharmacokinetic parameters will be calculated for the study drug:

1.  $C_{max}$  – maximum plasma concentration after the first and the fourth intravenous administration
2.  $T_{max}$  - time until  $C_{max}$  is reached
3.  $AUC_{(0-72)}$  – area under the plasma concentration curve from administration to 72 h after the first and the fourth intravenous administration.

$$AUC_{(0-72)} = \sum_{p=2}^{15} \frac{(C_p + C_{p-1}) * (t_p - t_{p-1})}{2},$$

где  $C_p$  plasma concentration at the moment  $t_p$  (hours);

$t_p \in \{ 0; 0.083; 0.167; 0.25; 0.33; 0,5; 0.75; 1; 2; 4; 8; 16; 24; 48; 72 \}; p=1, \dots, 15$

4.  $AUMC_{(0-72)}$  - the total area under the plasma concentration curve from administration to 72 h after the first and the fourth intravenous administration.

$$AUMC_{(0-72)} = \sum_{p=2}^{15} \frac{(C_p * t_p + C_{p-1} * t_{p-1}) * (t_p - t_{p-1})}{2},$$

где  $C_p$  – plasma concentration at the moment  $t_p$  (hours),

$t_p \in \{ 0; 0.083; 0.167; 0.25; 0.33; 0,5; 0.75; 1; 2; 4; 8; 16; 24; 48; 72 \}; p=1, \dots, 15$

5. Total clearance (CL) will be calculated as:

$$CL = \frac{DOSE}{AUC_{0-72}}$$

6. Mean Residence Time (MRT) will be calculated as:

$$MRT = \frac{AUMC_{0-72}}{AUC_{0-72}}$$

7. Apparent volume of distribution ( $V_d$ ) will be calculated as:

$$V_d = CL * MRT$$

8. Elimination rate constant ( $K_{el}$ ) will be calculated as:

$$k_{el} = \frac{1}{MRT}$$

9. Plasma concentration half-life ( $T_{1/2}$ ) will be calculated as:

$$T_{1/2} = \frac{\ln(2)}{k_{el}} = \ln(2) * MRT$$

10. Area under the plasma concentration curve from 0 to infinity ( $AUC_{(0-\infty)}$ ) will be calculated as:

$$AUC_{(0-\infty)} = AUC_{(0-72)} + \frac{C_{72}}{k_{el}}, \text{ где}$$

$C_{72}$ - plasma concentration of the drug during the 72 hours after the administration of the drug

11. The residual area will be calculated as:

$$\frac{AUC_{(0-\infty)} - AUC_{(0-72)}}{AUC_{(0-\infty)}}$$

Pharmacodynamics parameters

Based on determined hemoglobin level, reticulocytes counts, RBC counts, hematocrit a number of the pharmacodynamics parameters will be calculated for the study drug:

1.  $E_{max}$  – the maximum hemoglobin level (reticulocytes, RBC, hematocrit)
2.  $T_{max}$  - the time to the absolute maximum increase of hemoglobin level ( $E_{max}$ ) (reticulocytes counts, RBC, hematocrit)

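### The SAP's elimination constant is the reciprocal of an MRT cut off at 72 h, which caps T1/2 near 25 h and distorts the AUC(0-inf) tail and residual area; the protocol also mislabels AUC(0-inf) as AUC(0-168)

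*Protocol*

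**What the plan says.** **Endpoint name.** The protocol synopsis (PK Endpoints) describes a total area under the "curve from 0 to infinity" and attaches the symbol AUC(0-168). SAP 4.1 lists the endpoint as "area under the plasma concentration curve from 0 to infinity", with the infinity symbol. SAP 8.4 repeats it ("Area under the plasma concentration curve from 0 to infinity"). AUC(0-168) appears nowhere in the SAP, and SAP section 10 declares no deviations from the protocol. Neither document says whether the endpoint applies to the first injection, the fourth, or both.

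**Formulas (SAP 8.4).** The time grid ends "0.75; 1; 2; 4; 8; 16; 24; 48; 72" (hours). AUC(0-72) and AUMC(0-72) use the linear trapezoid. MRT is their ratio ("MRT = \frac{AUMC_{0-72}}{AUC_{0-72"), kel is 1/MRT, and T1/2 is ln(2) x MRT. AUC(0-inf) adds C72/kel to AUC(0-72), and the residual area is the share of AUC(0-inf) that this tail supplies.

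**Samples.** One PK sample falls 168 h after the first injection: "Visit 5 (Day 8): immediately before the second injection" (SAP 3.2; same in the protocol's Study Procedures). It enters no SAP formula. After the fourth injection the last PK sample is at 72 h. The Day 29 draw is listed for PD only.

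**Role.** The only stated equivalence limits, 80-125%, are for AUEC(1-29). SAP 8.2 nevertheless lists area under the curve, half-life and elimination parameters among the quantitative variables to be tested between groups.

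**The concern.** For a one-compartment intravenous bolus, 1/MRT equals the elimination constant only when MRT is integrated to infinity. Cut at 72 h, MRT omits the late part of the curve, which carries most weight in AUMC. So kel is too large, T1/2 too short and the added tail too small. The residual area normally tells the reader whether sampling went on long enough, and here it is computed with the same faulty constant, so it understates how much exposure lies beyond 72 h.

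The trial's stated purpose includes confirming equivalent pharmacokinetics. A formula that pulls two different half-lives toward a common ceiling makes the products look more alike in elimination than they are. The conflicting label adds a second problem: a reader cannot tell whether the protocol intended a measured area over one dosing interval or an extrapolated total.

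**Working it through.** **Inputs.** From SAP 8.4: the 15-point grid from 0 to 72 h and the formulas above. The documents give no half-life, so the values below are assumptions: noise-free mono-exponential decay from an initial concentration of 1, first injection. The plan prints no PK figure to reproduce. Its one design figure does reproduce (CV = 12.92/45.4 = 28.46%; power 80.95% at N = 56) and does not depend on these formulas.

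**Ceiling on T1/2, no half-life assumed.** For a flat curve, AUMC(0-72) = 72²/2 = 2592 and AUC(0-72) = 72, so MRT = 36 h. A declining curve puts more weight on early times, so MRT is at most 36 h and T1/2 at most ln(2) x 36 = 24.95 h. If the value at time 0 is a zero pre-dose sample, AUC falls by 0.083/2 to 71.96 and the ceiling moves only to 24.97 h.

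**Worked case, true half-life 25 h.**
- True rate = ln(2)/25 = 0.0277 per h; true AUC(0-inf) = 36.07; C72 = 2^(-72/25) = 0.1358.
- Grid values: AUC(0-72) = 31.71; AUMC(0-72) = 754.3.
- MRT = 754.3/31.71 = 23.79 h, so kel = 0.0420 per h and T1/2 = 0.693 x 23.79 = 16.5 h.
- Tail = 0.1358 x 23.79 = 3.23. The true tail is 0.1358 x 36.07 = 4.90.
- AUC(0-inf) = 31.71 + 3.23 = 34.95 before rounding of the parts; 34.95/36.07 = 0.969.
- Residual area = 3.23/34.95 = 9%; the true share beyond 72 h is 14%.

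**Across assumed half-lives.** The row before last keeps the 72 h grid and changes only kel, to a log-linear slope over 24, 48 and 72 h.

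| Assumed half-life (h) | 12 | 20 | 25 | 35 | 50 |
|---|---|---|---|---|---|
| SAP T1/2 (h) | 10.7 | 14.8 | 16.5 | 18.6 | 20.4 |
| SAP AUC(0-inf) / true | 1.04 | 1.00 | 0.97 | 0.90 | 0.79 |
| SAP residual area | 1% | 6% | 9% | 14% | 19% |
| True share beyond 72 h | 2% | 8% | 14% | 24% | 37% |
| AUC(0-inf) / true, fitted slope | 1.044 | 1.022 | 1.015 | 1.008 | 1.003 |
| Linear-rule AUC(0-168) / true AUC(0-168) | 1.07 | 1.09 | 1.08 | 1.07 | 1.05 |

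Adding a fast phase (half-life 1.5 h, carrying 30% or 50% of the initial concentration) changes the AUC(0-inf) ratios by less than 0.01.

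**Effect on the comparison.** Suppose one product has a 25% longer half-life and the same initial concentration, so both true ratios are 1.25.

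| Reference half-life (h) | 25 | 35 | 50 |
|---|---|---|---|
| SAP T1/2 ratio | 1.09 | 1.06 | 1.04 |
| SAP AUC(0-inf) ratio | 1.19 | 1.16 | 1.12 |

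At shorter reference half-lives the compression is milder: at 12 and 20 h the T1/2 ratio is 1.17 and 1.11, and the AUC(0-inf) ratio 1.23 and 1.21. If both products share one half-life, the error cancels in the ratio.

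**The case against.** The strongest reply is that nothing decisive hangs on this endpoint. AUC(0-inf) has no equivalence margin and no part in the sample size, and AUC(0-72) and Cmax head the PK list. That stands, and it limits the weight of the point.

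A second reply is that the size of the error rests on an assumed half-life. That stands for AUC(0-inf): the error vanishes near 20 h and turns slightly positive below it (6% too high at 8 h). It does not rescue T1/2, which is too short at every value tried and is capped whatever the data.

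Third, the wording in both documents agrees on infinity, so the 168 subscript may be a simple slip and not a second endpoint. That is fair. But 168 h is also the dosing interval and the time of the Day 8 pre-dose sample, so the intention cannot be settled from the text.

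A reader might also infer that exposure is misestimated because the 168 h sample goes unused. The arithmetic does not support that: a fitted slope on the same 72 h grid brings AUC(0-inf) within 2.2% at half-lives of 20 h and above. Adding the 168 h point under the SAP's linear trapezoid would instead overstate AUC(0-168) by about 5-9%.

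**Conclusion.** The kel formula is wrong for its purpose and should be changed. The cap on T1/2 near 25 h follows from the formula for any non-increasing curve. The other sizes depend on assumed mono-exponential decay: from 12 to 50 h, AUC(0-inf) runs from 4% too high to 21% too low, and at 50 h the residual area is reported as 19% where 37% is true.

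It would go too far to say that a difference in elimination would be hidden: it is attenuated, strongly for T1/2 and less so for AUC(0-inf). Nor do the documents support a claim that the AUEC(1-29) equivalence conclusion or the sample size is affected. What is affected is the secondary PK picture: T1/2, kel, AUC(0-inf), the residual area and the between-product comparison of these.

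The label conflict is a separate, textual defect and needs no assumption.

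**What to change.** 1. In SAP 8.4, estimate kel by log-linear regression of the terminal points: 24, 48 and 72 h, plus the Day 8 pre-dose sample at 168 h for the first injection where it is quantifiable. At a 25 h half-life that concentration is about 1% of the initial value (2^(-168/25) = 0.0095), and the documents give no quantification limit, so the rule must cover values that cannot be quantified. Use this kel for T1/2, AUC(0-inf) and the residual area.
2. Correct the symbol in the protocol synopsis so that both documents name the same endpoint, and state which dose or doses it covers.
3. State whether the Day 8 sample enters the first-dose AUC. If it does, use a log trapezoid from 72 to 168 h. Replacing AUC(0-inf) with AUC(0-168) for the first dose is optional and is not needed to cure the error.
4. After the fourth injection no 168 h PK sample exists, so label AUC(0-inf) there as extrapolated.

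The cost is one revised formula, one corrected label and a few sentences. No further blood draws are required.

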
Study Design
	
Clinical study BCD-066-3 is a double-blind controlled, randomized, parallel-group study of the pharmacokinetics, pharmacodynamics, tolerability, and safety of repeated-dose intravenous BCD-066 and Aranesp[®].
 
The study is planned to include 62 healthy male volunteers (56 active participants and 6 back up subjects to replace dropouts). Before inclusion in the study, all potential participants are given full information about the study. This information is presented in the Participant Information Sheet. If the potential participant gives his consent to be in the study, he has to sign the Informed Consent Form for participation in a clinical study and then undergo a 14-day screening examination to confirm that he is eligible for the study.
 
After passing the screening and being considered eligible for the study, subjects are centrally randomized at a 1:1 ratio to one of two treatment groups (#1 and #2). Subjects in Group #1 will receive IV injections of 1.0 µg/kg BCD-066 on Day 1, Day 8, Day 15, and Day 22. Subjects in Group #2 will receive IV injections 1 µg/kg Aranesp[®] on Day 1, Day 8, Day 15, and Day 22. This is a double-blind study, which means that neither the investigator nor the subject will know what drug is used in each group.
 
Blood samples for evaluation of darbepoetin alfa concentration will be collected 30 min, 20 min, and 10 min before the injection, immediately before the injection (not more than 5 min before drug administration), and then 5 min, 10 min, 15 min, 20 min, 30 min, 45 min, 1 h, 2 h, 4 h, 8 h, 16 h, 24 h, 48 h, and 72 h after the first and the fourth IV injection. There will be 4 blood collections before and 14 blood collections after the first and the fourth IV injection of darbepoetin alfa. The serum concentrations will be used to calculate the key PK parameters of darbepoetin alfa. Before the second and the third injection, blood samples will be collected only once. During the entire study, there will be 38 blood collections for PK evaluation.
 
Blood samples for evaluation of hemoglobin (the primary PD endpoint) and secondary PD parameters (reticulocytes, RBC, hematocrit) will be collected before each injection of the test drug/reference drug, then 1 day, 3 days, and 5 days after the first, second, and third injection, and 1 day, 3 days, and 7 days after the fourth injection. Two more blood collections will be performed for immunogenicity assessment (at screening and on Day 29).
 
This study includes a screening examination (not more than 14 days) and 16 study visits. After the first and fourth injection of the test/reference drug, all volunteers will be required to stay in the clinic for at least 24 h for monitoring purposes. The duration of the study from the first drug injection to the final visit is 29 days.
 
Special requirements to volunteers

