	
 • Visit 7 (Day 11): 240 h after the first injection (3 days after the second injection). • Visit 8 (Day 13): 288 h after the first injection (5 days after the second injection). • Visit 9 (Day 15): 336 h after the first injection (immediately before the third injection). • Visit 10 (Day 16): 360 h after the first injection (one day after the third injection). • Visit 11 (Day 18): 408 h after the first injection (3 days after the third injection). • Visit 12 (Day 20): 432 h after the first injection (5 days after the third injection). • Visit 13 (Day 22 – Day 23): 504 h after the first injection (immediately before the fourth injection); 528 h after the first injection (one day after the fourth injection). • Visit 15 (Day 25): 576 h after the first injection (3 days after the fourth injection). • Visit 16 (Day 29): 672 h after the first injection (7 days after the fourth injection). 
Safety monitoring procedures:
 
For safety evaluation, the study team will monitor vital signs (BP, pulse, respiration rate, and body temperature), perform regular physical examinations including assessment of the injection site, and run hematology and chemistry tests, blood tests for anti-darbepoetin alfa binding and neutralizing antibodies, urinalysis, and ECG.

Total Study Duration
	
Expected study duration is 2 years including up to 18 months of enrollment and 6 months of data collection and statistical processing.
 
Each study subject is expected to be in the study for 64 days, which includes the screening (14 days), administration of the test/reference drug and investigation of the PK and PD (29 days), and the follow-up period (Day 30 to Day 50).

PK Endpoints
	
 • Endpoints: 
 – The area under the Time vs. Concentration curve for darbepoetin alfa from injection to 72 h ($AUC_{(0-72)}$) after the first and the fourth IV injection of BCD-066 or Aranesp[®] – The maximum concentration of darbepoetin alfa in the serum after the first and the fourth IV injection of BCD-066 or Aranesp[®] (C_{max})

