	
The PD analysis will include all subjects who have received all doses of the test/reference drug as per protocol.
 
Not more than 3 PD blood collections can be missed over the entire study. Subjects who have two consecutive blood samples missed will be not included in the analysis.
 
The PD analysis will be based on the hemoglobin concentrations, reticulocyte and RBC counts, and hematocrit. The limiting hemoglobin level in this study is 180 g/L. If the subject reaches this level before the last injection of darbepoetin alfa, he will be withdrawn from the study. If the subject reaches the limiting Hb concentration after he receives the last (fourth) injection of darbepoetin alfa, he will not be withdrawn from the study.

Safety Assessment
	
Endpoints:
 
 • The proportion of subjects who developed AE(s) after receiving at one injection of darbepoetin alfa • The rate of SAEs • The rate of CTCAE grade 3/4 AEs • The rate of withdrawals due to AEs • The proportion of subjects who had injection site reactions • The proportion of subjects who had antibodies to darbepoetin alfa on Day 29. 
Methods used for safety assessment:
 
The safety analysis will include all subjects who have received at least one dose of the test/reference drug.
 
The safety will be analyzed based on the information about:
 
 – The reported AEs/SAEs, – Results of physical examinations with an assessment of the injection site, vital signs, and instrumental and laboratory test results (hematology and chemistry, blood testing for binding and neutralizing anti-darbepoetin alfa antibodies, and urinalysis).

Statistical Analysis
	
Determination of sample size
 
The sample size was determined using the variation coefficients for hemoglobin increase (Hb AUEC) obtained by Cheung, 2001¹. The estimated Type I error was 5% ($\alpha=0.05$) and Type II error was 20% ($\beta=0.2$), with the test power of 80%.
 
The sample size was calculated with the “sampleN.TOST” function of the “PowerTOST” package for R. The calculation used the CV values and the ratios of the mean Hb increases (AUEC). The study

¹ W.Cheung, N. Minton, K.Gunawardena. Pharmacokinetics and pharmacodynamics of epoetin alfa once weekly an three times weekly, 2001

should include 28 subjects per group and 6 subjects as backups to replace potential early withdrawals (62 volunteers total).

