### **Safety analysis**

The safety analysis will include all volunteers who have received one dose of the test/reference drug.

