### **Immunogenicity analysis**

The immunogenicity analysis will include data of all volunteers who have received one dose of BCD-066 or reference drug. If a subject has had serum samples taken on Day 1 and Day 29 missed / lost / spoilt, his data will not be included in the immunogenicity analysis.

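### A man who reaches 180 g/L before dose 4 leaves the study, not just the injections, so he has no Day 29 antibody result

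*Protocol*

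**What the plan says.** Under PD Endpoints (methods for pharmacodynamic assessment), the protocol synopsis states: "The limiting hemoglobin level in this study is 180 g/L". It continues: "If the subject reaches this level before the last injection of darbepoetin alfa, he will be withdrawn from the study". A man who crosses the limit after the fourth injection is not withdrawn.

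On antibodies, the synopsis (Study Design) says: "Two more blood collections will be performed for immunogenicity assessment (at screening and on Day 29"). SAP section 3.1 repeats this. The endpoint under Safety Assessment is: "The proportion of subjects who had antibodies to darbepoetin alfa on Day 29". It also appears in SAP section 4.3.

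On who is analysed, SAP section 7 says: "The safety analysis will include all volunteers who have received one dose of the test/reference drug". The protocol's rule is at least one dose. The immunogenicity paragraph of SAP section 7 leaves a man out under this condition: "If a subject has had serum samples taken on Day 1 and Day 29 missed / lost / spoilt".

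On duration, the synopsis says: "Each study subject is expected to be in the study for 64 days". That total includes Day 30 to Day 50. Nothing is said about whether it applies to a man withdrawn under the hemoglobin rule.

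**The concern.** Stopping injections at 180 g/L protects the volunteer and is not in question. Nor is the different rule after dose 4, when no injection is left to stop. The problem is that the rule joins two decisions, ending treatment and ending observation, and only the first is needed for protection.

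Two things are at stake. First, comparing safety and tolerability is one of the three stated objectives, and antibody status on Day 29 is one of its endpoints. The rule removes that result for certain men. Second, these men are selected by what the drug did to them: they crossed the plan's own limit while dosing was under way. Missing data that depend on response are less benign than a lost tube. These are also the volunteers for whom the remaining hemoglobin and safety checks are most useful.

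**Working it through.** **Step 1: timing.** Doses are on Days 1, 8, 15 and 22. Antibody blood is drawn at screening and on Day 29. A withdrawal before dose 4 happens on Day 22 at the latest, so it always comes before the only post-exposure sample. A man withdrawn on Day 22, 20 or 18 leaves 7, 9 or 11 days before it.

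**Step 2: what is lost and what is kept.**
- Lost: the Day 29 antibody result and, on the synopsis wording, the remaining scheduled safety visits.
- Kept: adverse events up to withdrawal, because one dose places him in the safety set.
- Unchanged: his PD-set status. That set requires all doses, so he is outside it either way.
- Not recovered later: SAP section 8.3 does not substitute missing data.

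**Step 3: the plan's own figure.** The SAP has no figure for hemoglobin withdrawals. Its sample-size figure reproduces: CV = 12.92/45.4 = 28.46%; with 28 per group, a true ratio of 1, limits of 80–125% and α = 0.05 for each one-sided test, power is 80.955% against 80.95% stated. Nothing here disputes it.

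**Step 4: can the number of men be estimated?** Entry hemoglobin is 120–150 g/L, so the limit needs a rise of 30 to 60 g/L. The SAP gives a hemoglobin AUEC of 45.4 (SD 12.92) from a cited epoetin alfa study, with no unit or time window. Assume g/dL × day over 28 days, transfer to this drug and dose, a normal distribution and a linear rise. Then:

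- AUEC = slope × 28²/2 = slope × 392.
- Reaching 180 g/L by t days after dose 1 needs AUEC ≥ 392 × (180 − Hb₀)/10/t.
- Example: Hb₀ = 150 and t = 21 (Day 22) needs 392 × 3/21 = 56.0, so z = (56.0 − 45.4)/12.92 = 0.82 and the probability is 21%. For Hb₀ = 140 it needs 74.7, so z = 2.27 and the probability is 1.2%.

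The Visit 13 sample is timed at "504 h after the first injection (immediately before the fourth injection"). Whether its result is read before dosing is not stated, so both cases are shown, averaged over uniform baselines:

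| Case | Baseline 120–150 g/L | Baseline 140–150 g/L |
|---|---|---|
| Day 22 result read before dosing (t = 21) | 2.7% (1.5 of 56) | 7.7% (4.3 of 56) |
| Not read; last usable result Day 20 (t = 19) | 1.0% (0.56 of 56) | 3.0% (1.7 of 56) |

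Scaling the mean and SD by 0.75 to 1.25 spreads these from 0.01% to 31%. Shape matters too. Holding AUEC fixed and letting the rise follow t^k, the 2.7% becomes 0.6% at k = 0.5 and about 6.5% at k = 2. The central values suggest a handful of men at most, but the range is too wide to serve as an estimate.

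**Step 5: effect on precision.** With no antibodies seen in an arm of n, the one-sided 95% upper bound is 1 − 0.05^(1/n).
- Without replacement: 10.1% (n = 28), 10.5% (27), 10.9% (26).
- With replacement: back to 10.1%.
- If all 62 were randomised at the start, 31 per arm: 9.2%, and 9.5% or 9.8% after one or two losses.

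Precision is barely touched in any of these cases.

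**The case against.** The strongest reply is that the available protocol text is a synopsis. An early-termination visit, an exit blood sample or follow-up of adverse events after withdrawal could be set out elsewhere, and the 64-day expectation is worded for every subject. This stands in part. A reader might infer that withdrawn men are left unobserved. The documents do not show that; they only fail to say how such men are followed. What does follow from the wording is that a man out of the study before Day 22 dosing has no Day 29 sample.

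Second, six backups are planned to replace withdrawals, and even the 4.3 men in the high case of the table are fewer than six. This stands for arm size and precision. It does not recover the withdrawn man's own result or undo the selection.

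Third, harm to the comparison is conditional. A reader might infer that the antibody comparison is biased. That would need the products to differ in how fast hemoglobin rises, and fast responders to differ in antibody status. The documents support neither.

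Fourth, keeping him does not produce an equivalent result. A full-course man is sampled 7 days after dose 4; a man stopped on Day 22 would be sampled 14 days after dose 3. This is correct, and the fix has to flag it.

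Finally, the SAP's immunogenicity rule names a Day 1 sample that the schedule does not contain, and names it jointly with Day 29. It is therefore not clear that this man would be excluded from that analysis. That wording issue affects every subject and adds no weight here.

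**Conclusion.** The point holds as a cheap improvement, worth considering. By its own terms the rule removes the Day 29 antibody result from any man who reaches 180 g/L before dose 4 and, on the synopsis wording, ends his remaining scheduled safety visits. The loss is tied to response.

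Its size is not given and is probably small. The percentages above rest on an assumed unit, time window, curve shape, baseline distribution and transfer from another drug, and should not be quoted as a rate.

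Three stronger conclusions are not supported. The primary equivalence conclusion is not affected, since such a man is outside the PD set with or without the change. His adverse events up to withdrawal are not lost. The antibody comparison is not shown to be imprecise or biased. If a fuller protocol already provides post-withdrawal follow-up with an antibody sample, confirming that would close most of the point.

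**What to change.** **Protocol, PD Endpoints, methods for pharmacodynamic assessment.** Keep the 180 g/L limit and the dosing stop. Replace withdrawal from the study with: no further injections; the man stays for the scheduled safety and hemoglobin checks, the Day 29 antibody sample and the Day 30 to Day 50 follow-up, unless he withdraws consent. If he leaves, an antibody sample is taken at exit.

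**SAP section 7, immunogenicity analysis.** Include his Day 29 result by arm, flagged as following fewer than four doses. List exit samples separately, because they are not Day 29 results. Count men with no post-dose sample as missing, by arm. PD-set membership does not change.

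**Cost.** A sentence or two in the protocol and a short addition to SAP section 7. The visits and the Day 29 sample are already scheduled; only the exit sample is new. The downsides are that a few men attend visits without being dosed, and that their antibody results reflect fewer doses and a longer gap since the last one.
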